### **7.2.2 CDC Laboratory Management**

The CDC lab will send results back to Duke University using secure data transfer methods. CDC will send any remaining serum samples back to the site(s) after completing the pertussis testing or disposed at the request of the Sponsor. CDC pertussis laboratory will destroy unused DBS after all assays and the study have been completed. CDC laboratory staff will be blinded to the vaccination status of the samples being tested.

### **7.3 Role of the CDC Investigators in the Project**

This study is funded by a CDC contract with Duke University and Cincinnati as Task Orders in the CISA Project Contract; the National Vaccine Program Office (NVPO) has also provided funding. The Duke University PI ([name]) will oversee the study in partnership with the Cincinnati PI ([name]). The NVPO and CDC staff will collaborate with both sites to develop the protocol, conduct the study, ensure the study is aligned with US Department of Health and Human Services (CDC and NVPO) public health priorities, and analyze the data and disseminate the results. CDC may receive access to coded data not containing any directly identifying information. The CDC lab will conduct pertussis immunogenicity testing for the maternal serological samples and infant DBS collected in the study.

## **8 HUMAN SUBJECTS**

### **8.1 Human Subjects Involvement, Characteristics, and Design**

Duke and Cincinnati investigators will be responsible for submitting the protocol, informed consent (Appendix I), memory aids (Appendix B-E), recruitment letters, flyers (Appendix G-H), and any written or verbally conveyed materials (Appendix A and F) specific to this project to their institutional review boards. CDC staff will be responsible for submitting materials to the CDC IRB for review and approval.

To facilitate subject recruitment at the practices, we will request a waiver of consent and HIPAA authorization for ascertainment (identification, selection) and/or recruitment of potential subjects while recording identifiable private health information (PHI) prior to obtaining the subject's consent. This information will be obtained from review of the

electronic scheduling and medical record systems in the clinics in order to determine eligibility for study enrollment. We will review information only the minimum amount of information necessary to determine eligibility, i.e. date of birth, current pregnancy status, pregnancy history, medical and surgical history, ultrasounds pertaining to current pregnancy, and recent laboratory test results. The PHI collected prior to consent will be used to recruit and screen only. Use of PHI in this manner involves no more than minimal risk to subjects and no information will leave the study sites.

Continuing reviews will be submitted to the IRBs on an annual basis. Protocol deviations or concerns about study integrity will be reported promptly to the overseeing IRB in accordance with institutional requirements.

### **8.2 Sources of Material**

Medical history and immunization history will be obtained from the medical record and from patient report. Demographic information will be obtained from the medical record and patient report. Subjects will record solicited adverse reactogenicity events and any medical intervention sought on the day of and 7 days following vaccinations (or 7 days following mock vaccination) on the memory aid (Appendix B-E). Memory aid information will be reported to the study team during a telephone call or in the web-based REDCap system. The research staff will assess one or more of the following: weight, height, temperature, blood pressure, and pulse.

### **8.3 Potential Risks and Benefits**

Tdap and IIV are FDA licensed vaccines approved for use in non-pregnant individuals and are not contraindicated for use in pregnant women. Both vaccines are standard clinical practice and recommended by the CDC and ACOG during pregnancy. Participants will be provided with the CDC Vaccine Information Statements (VIS) for IIV and Tdap.

IIV risks include minor problems such as soreness, redness, swelling, or pain where the shot was given, hoarseness, sore, red or itchy eyes, cough, fever, aches, headache, itching, fatigue, all of which usually occur within 1-2 days of vaccination and are self-limiting. Syncope (fainting) can occur in association with administration of injectable vaccines. More serious problems including a small increased risk of Guillain-Barré Syndrome estimated at 1 or 2 additional cases per million people vaccinated. This is much lower than the risk of severe complications from influenza infection, which can be prevented by IIV. In addition, any medication can cause a severe allergic reaction, or anaphylaxis, which is estimated at ~ 1 in a million doses of IIV (<http://www.cdc.gov/vaccines/hcp/vis/vis-statements/tdap.html> and <http://www.cdc.gov/vaccines/hcp/vis/vis-statements/flu.html>).

Tdap risks include mild problems such as redness, swelling, and pain where the shot was given, redness or swelling where the shot was given, fever, chills, sore joints, headache, body aches, fatigue, nausea, vomiting, diarrhea, stomach ache, rash, and swollen glands, all of which usually occur within 1-2 days of vaccination and are self-limiting. Moderate problems include higher severity of mild problems and swelling of the entire arm in which the injection was given. Rarely, local injection site symptoms limit the ability to perform usual activities and require medical attention.

Problems that could happen after any injected vaccine:

- People sometimes faint after a medical procedure, including vaccination. Sitting or lying down for about 15 minutes can help prevent fainting, and injuries caused by a fall. Subjects should inform their doctor should they feel dizzy, or have vision changes or ringing in the ears.
- Some people get severe pain in the shoulder and have difficulty moving the arm where a shot was given. This happens very rarely.
- Any medication can cause a severe allergic reaction. Such reactions from a vaccine are very rare, estimated at about 1 in a million doses, and would happen within a few minutes to a few hours after the vaccination. As with any medicine, there is a very remote chance of a vaccine causing a serious injury or death.

There is a small risk of infection around the heel stick where the blood was collected. Maternal subjects may also experience dizziness or fainting. Each maternal subject will be asked to have up to 3 blood samplings with the total volume not to exceed 45mL. For infants participating in the 2-month study procedure, the volume of blood collected will be no more than 0.5 ml. There is no risk to the subject or their newborn for collection of cord blood, as the cord blood is drawn from the umbilical cord/placenta after the baby is not attached to it.

Randomized controlled trials of IIV during pregnancy have demonstrated efficacy in preventing maternal influenza infection as well as infant influenza infection for the first 6 months of life. Further, these trials have not demonstrated any concerns for maternal-fetal-infant safety. Studies of Tdap during pregnancy have demonstrated an appropriate maternal immune response but have been too small to evaluate efficacy. A recent large scale observational study of Tdap during pregnancy, demonstrated a reduction in neonatal/infant pertussis, which has been further supported by a recent retrospective case-control study. Studies of Tdap in pregnancy have not demonstrated any concerns for maternal-fetal-infant safety. However, as with any vaccines we cannot assure or guarantee protection against influenza, tetanus, diphtheria, or pertussis given the potential for mismatch between circulating influenza vaccine strains and those included in the 2016-2017 and 2017-2018 vaccines and variation in individual immune responses.

The Advisory Committee on Immunization Practices (ACIP) does not make specific recommendations about simultaneous or sequential administration of Tdap and IIV for pregnant women. However, based on the ACIP Best Practice Guidelines for Immunization, Tdap and IIV (both inactivated vaccines) may be administered to pregnant women either simultaneously or sequentially (ACIP Best Practice Guidelines for Immunization accessed at <https://www.cdc.gov/vaccines/hcp/acip-recs/general-recs/index.html>)

1. Simultaneous administration of vaccines is defined as administering more than one vaccine on the same clinic day, at different anatomic sites, and not combined in the same syringe. Experimental evidence and extensive clinical experience provide the scientific basis for administering vaccines simultaneously. Simultaneously administering all vaccines for which a person is eligible at the time of a visit increases the probability that a child, adolescent, or adult will be vaccinated fully by the appropriate age.

Tetanus toxoid, reduced diphtheria toxoid, and acellular pertussis (Tdap) and quadrivalent inactivated influenza vaccine can be administered simultaneously.

There is the potential risk of loss of confidentiality about information obtained as part of this study.

#### **8.4 Adequacy of Protection Against Risks**

##### **8.4.1 Protections against Risk**

Subjects will be counseled on possible side effects following vaccination and followed closely during the 7 days post-vaccinations for assessment of moderate to severe local or systemic reactogenicity. Subjects will be evaluated and cared for as described in the *Unscheduled Visit* section above. All subjects will be monitored in a sitting or lying position for 20 minutes following vaccinations to help prevent fainting, and injuries caused by a fall. Subjects with a prior history of any reaction following either IIV or Tdap will be excluded from study enrollment.

Every effort possible will be made to keep information about participants confidential. Computerized participant information will be kept in password protected files on secured servers. Paper case report forms will be kept in locked files belonging to the study personnel. Any publications resulting from this work will not contain any identifiable participant information.

##### **8.4.2 *ClinicalTrials.gov* Requirements**

The project is registered on *ClinicalTrials.gov*. (NCT02783170).

#### **8.5 Human Subjects**

In obtaining and documenting informed consent, the Investigator and study team will comply with the applicable regulatory requirements, Good Clinical Practices, and ethical principles. The written informed consent form must be signed and dated by the study participant prior to initiation of any study activities.

##### **8.5.1 Vulnerable Subjects Research**

###### **Vulnerable subjects**

This study proposes to include pregnant women and neonates.

###### **Pregnant women**

Tdap and IIV are FDA licensed vaccines and are recommended by the CDC and ACOG during pregnancy, however the risks for both vaccines are listed in section 8.3.

The specific procedures to be performed as part of this study are limited to minimal blood draw (<50mL over an 8-week period and not more than twice in a 7-day period), and other non-invasive procedures that are commonly performed during routine physical exams and are considered safe for pregnant women. These procedures do not pose greater than minimal risk to the fetus. Collection of the placenta for research purposes following delivery of the fetus will be conducted in accordance with 45 CFR 46.206.

This study will involve only those women who have given their free and informed consent in accordance with 45 CFR 46.116 and has the prospect of direct benefit to both the mother and infant. Randomization of vaccine administration provides minimal risk to the subject and fetus as these vaccines are routinely given either sequentially or simultaneously during pregnancy and do not go beyond the scope of standard of care.

The small amount of blood that will be drawn during the duration of pregnancy (up to 45 ml) are considered safe and are not expected to cause any harm to the baby. No inducement, monetary or otherwise, will be offered to terminate a pregnancy. Individuals engaged in the research will have no part in any decisions as to the timing, method or procedures used to terminate a pregnancy, or in determining the viability of a neonate.

**Infants**

Identifiable private information will be collected about the infants at the time of delivery. Significant infant complications identified during the delivery visit will be followed up to 60 days of life.

Mothers will be informed about the infant data collection at the time they consent for the study, and thus, the consent form for pregnant women will also serve as the parental permission for including the infant as a subject after delivery. A separate consent form will be used to obtain informed consent from pregnant or postpartum mothers or fathers for collection of an infant blood sample and documentation of any history of pertussis illness at 2-months of age. These procedures do not pose greater than minimal risk to the infant.

## Appendix A: Memory Aid Instructions

### **HOW TO COMPLETE THE MEMORY AID**

#### **Completing the Memory Aid**

- Complete the Memory Aid every evening, starting the day of vaccination (Day 1) and continuing through Day 8. (Example: If you received your vaccination on Monday, you would start your memory aid Monday evening and finish your memory aid on the following Monday evening.)
- Assess symptoms and fill out the Memory Aid in the evening (after 4:00pm, but before midnight).
- For each symptom you experience, you must record the maximum severity and/or measurement.
- Fill out all the spaces each time. If you don't have any symptoms, write 0 in all the boxes.
- Record any other symptoms or medical problems that you have each day under the "other symptoms" portion of the Memory Aid.
- Record all new medications and any changes to previously reported medications that you take each day on page 3 of the Memory Aid.
  - You do not need to enter any regular medications you have already told us about. If you take a new medication, change a medication you were already on, or take something for comfort, please enter this information on the Memory Aid.
- Record any visits to the Emergency Room, Urgent Care, Labor and Delivery, or doctor's office (other than for a routine checkup or prenatal care) on the last page of the Memory Aid.
- Complete the Memory Aid for days 1-8 after vaccination.
- Be sure to return the paper Memory Aid to the study team at the next scheduled study visit.

### **HOW TO TAKE MEASUREMENTS**

#### **Temperature**

- Measure your temperature at approximately the same time each day or when you feel feverish.
- Do not eat, drink, or smoke for 10 minutes prior to taking your temperature.
- To use the thermometer, place the skinny end of the thermometer under your tongue toward the back of your mouth and press the button to turn it on (it will beep).
- Keep your mouth closed and the thermometer still until the thermometer beeps rapidly, indicating completion.
- Record the temperature displayed on the screen.
- If your temperature is less than 97.0°F wait approximately 10 minutes and retake again. Record the highest temperature.
- If your temperature is at or above 100.0°F high, repeat approximately 20 minutes later to verify. Record the highest temperature.
- If multiple temperatures are measured during one day, record the highest temperature on the Memory Aid.

**Measuring Swelling and Redness at the Site of the Vaccination**

- Use the ruler that the study staff has given you and record the measurements in millimeters (mm).
- Follow these instructions to measure the size of the area with swelling or redness.
  - Determine the widest part (or diameter) of the area. Redness and swelling are often not in a perfect circle, so it is important to measure where it is the widest.
  - Measure this distance with the ruler and measure in **millimeters (mm)** by counting the small hash marks.
  - Measure the swelling and redness separately and record on the memory aid under the local vaccination site reactions.

**CONTACT THE RESEARCH TEAM AND/OR DOCTOR if...**

- If you have **any severe symptoms** (grade 3). These are any symptoms that **prevents daily activity and/or requires medical care and/or missing work/school**.
- If you have any other symptoms or health complaints of concern, even if they are not the events listed on the Memory Aid.
- Please note that if you feel you are experiencing a life threatening reaction or emergency, please call 911 or go to your nearest emergency room to seek treatment. Once everything is safe, you can then contact the research team about your reaction or emergency.
- If you have any concerns or questions about completing the Memory Aid or about symptoms you are experiencing, please contact the study team at the number below:

Contact name: \_\_\_\_\_ Phone #: \_\_\_\_\_

Appendix B: Memory Aid for Simultaneous Group – Visit 1

CISA Tdap/IIV Data Collection Form  
Memory Aid Simultaneous Group  
TI07A

Subject ID: \_\_\_\_\_

Please assess symptoms and fill out memory aid in the evening (after 4pm)

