### ***Unscheduled Clinic Visit***

- Unscheduled visits would be conducted for study participants with severe local or systemic reactions with assessment including vital signs, direct measurement of the extent of local reactions, and photographs of local reactions. Providers will be informed of the reactions in their patients and direct care as needed. Study staff will review the memory aid data (if applicable) and record any AEs, SAEs, concomitant medications, and current medical/pregnancy status as described in Section 5.1.

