### **5.3 Reactogenicity Assessment**

Frequency and occurrence of local and systemic reactogenicity, solicited and unsolicited AEs, SAEs, concomitant medication use, and unscheduled medical care will be assessed immediately after vaccination (day 1) through post-vaccination Day 8 (day 1-8) using a standard memory aid (Appendix B-E). At the time of study enrollment, participants will be given an oral digital thermometer and instructed on completing the memory aid to document oral temperatures and post-injection symptoms, daily. A study staff member will review each portion of the memory aid with the subject in order to familiarize the subject with the form. The subject will be given the choice of either entering their data into REDCap daily or utilizing a traditional paper memory aid. Subjects will be instructed to notify study staff promptly using the 24-hour contact number provided in the memory aid in the event of any severe (Grade 3) local or systemic reactions.

Beginning on the evening of Study Visit 1 (Day 1) following vaccination, participants will record their oral temperature using the study-supplied thermometer, the occurrence of AEs, and concomitant medication use for the next 7 days (Day 1 – 8). Temperature will be recorded at roughly the same time each day. If a temperature  $\geq 100.0^{\circ}\text{F}$  ( $37.8^{\circ}\text{C}$ ) is recorded, a second measurement will be taken within 20 minutes. If more than one temperature is taken on the same day, the highest temperature should be recorded. Solicited adverse events (local and systemic), which will be classified as mild, moderate, or severe as described in **Tables 3 and 4**, will be reviewed and recorded during Visits 2-3 and 5-6.

Each day, women will record reactogenicity data either on paper or directly into the REDCap system through 7 days post-vaccination. All subjects will be provided with a paper memory aid (Appendix B-E) to record their reactogenicity data for ease of recall when entering into REDCap or recalling to research staff over the phone. We have selected a reactogenicity period of vaccination day and the next seven days based on pre-licensure studies of Tdap and IIV vaccines in adults and adolescents which suggest

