that the onset of solicited, local adverse events is highest during days 1 through 4 post-vaccination. Moreover, pre-licensure data indicate a low incidence of late onset reactions (> 3 days post-vaccination). Contemporary evaluations of booster doses of both licensed Tdap vaccines (i.e., Boostrix and Adacel) have used either 4- or 7-day periods for assessments of reactogenicity citing that most local and systemic reactions occur within the first 48 hours after vaccination.

Women using REDCap will receive an email soliciting their record of events (daily link is sent via email for subjects to complete). The REDCap system provides real-time reports regarding who has responded. Local and systemic reactogenicity will be measured as described in **Tables 3 and 4** and subjects will contact the study team if they have any severe solicited symptoms or experience an SAE. AEs and SAEs will be reviewed in REDCap or by phone follow-up. For severe symptoms in REDCap, study team will follow-up with the subject by phone to gather more information about the symptoms.

Table 3: Injection-site Reactogenicity			
Symptom	Mild (Grade 1)	Moderate (Grade 2)	Severe (Grade 3)
Pain (without touching)	Noticeable but does not interfere with activity	Interferes with activity but did not necessitate medical visit or absenteeism	Prevents daily activity and/or resulted in medical visit and/or absenteeism
Pain upon touching (Tenderness)	Noticeable but does not interfere with activity	Interferes with activity but did not necessitate medical visit or absenteeism	Prevents daily activity and/or resulted in medical visit and/or absenteeism
Swelling (Induration)	<10 mm	10-34 mm	>=35 mm
Redness (Erythema)	<10 mm	10-34 mm	>=35 mm

Participants will also be queried during Visits 2-3 and Visits 5-6 on common post-vaccination local and systemic symptoms as described in **Tables 3 and 4**.

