**Visit 4**

Please assess symptoms and fill out memory aid in the evening (after 4pm)

Post-Visit Day Date (dd/MM/yyyy) Oral Temperature °F	Day 1 (Day of visit)	Day 2	Day 3	Day 4	Day 5	Day 6	Day 7	Day 8
General Systemic Symptoms:								
Grade 0 = None								
Grade 1 = Mild (noticeable but does not interfere with activity)								
Grade 2 = Moderate (interferes with activity but did not need a medical visit or absenteeism [i.e. missing work or school])								
Grade 3 = Severe (prevents daily activity and/or resulted in medical visit and/or absenteeism [i.e. missing work or school])								
Chills/Shivering								
Fatigue								
Body Aches								
Headache								
Joint pain								
Nausea								
Vomiting								
Diarrhea								
Abdominal Pain								
Body rash								

CISA TDAP/IV Data Collection Form  
Memory Aid Simultaneous Group  
TT09A

Subject ID: -----

Other symptoms			
1 = Mild (noticeable but does not interfere with activity or measurement) Grade 2 = Moderate (interferes with activity but did not need a medical visit or absenteeism [i.e. missing work or school]) Grade 3 = Severe (prevents daily activity and/or resulted in medical visit and/or absenteeism [i.e. missing work or school]) Other symptoms to report:  None			
Symptom	Intensity: Mild, Moderate or Severe	Start date	Stop date

Medications					
New medications used following vaccination or changes to previously reported medications:  No  Yes (complete chart below)					
Medication name	Dose	Frequency	Start date	Stop date	Reason

Any visit to the Emergency department (ED), Urgent Care, Labor and Delivery, or doctor's office other than routine check-up or prenatal visit?  No  Yes (please explain below and add dates of the visit to ED, Urgent Care, Labor and Delivery, or doctor's office)

---

---

---

Appendix E: Memory Aid for Sequential Group – Visit 4

CISA Tdap/IIV Data Collection Form  
Memory Aid Sequential Group  
TI09B

Subject ID: \_\_\_\_\_

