## Appendix F: Phone Script

## CISA TDAP/IIV Memory Aid Phone Script

To be used for visits: 2, 3, 5, 6, & 7

Hello, my name is \_\_\_\_\_ calling from the Tdap and Flu vaccine study at \_\_\_\_\_. I would like to review your memory aid information since your most recent study vaccination(s). This call should only take a few minutes. Is now a good time to review this information with you? Do you have your memory aid available to review with me?

Starting from day \_\_\_\_, please provide me with the temperatures that you recorded so far.

Starting with day \_\_\_\_, please tell me if you have recorded any reactions other than 0 (none). If so, in what category/ies? What number(s) did you record for the reactions? Did any of your symptoms prevent you from doing your daily activities or going to work/school?

Next on day \_\_\_\_, please tell me if you have recorded any reactions other than 0 (none). If so, in what category/ies? What number(s) did you record for the reactions? (*continue to ask for each day until all completed days have been reviewed with the subject*). Did any of your symptoms prevent you from doing your daily activities or going to work/school?

Did you report any other symptoms on your memory aid? Please provide me with the symptom, what you rated it, as well as the start and stop dates. (*continue to ask for any additional other symptoms*)

Did you take any new medications or change any of your current medications since you were vaccinated for the study? Please provide me with the medication name, dose, how often you took it, start and stop dates, and why you took the medicine.

Did you have any visits to the emergency room, urgent care, labor and delivery, or unplanned visits to the doctor's office, other than routine check-ups? If yes, please explain.

That concludes our study follow up call. Your next study visit is planned for: \_\_\_\_\_. Please remember to bring your memory aid with you to that visit so that we can place it in your study file.

Do you have any questions at this time? Please do not hesitate to contact the study team if you have any questions or concerns. We can be reached at \_\_\_\_\_.

Thank you for your continued study participation. Have a wonderful day.

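### The Appendix A call box describes Grade 3 only in functional terms, so it omits the size and temperature limits that define Grade 3 for swelling, redness and fever

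*Combined protocol and SAP*

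**What the plan says.** Section 5.3 says subjects will be instructed to notify staff promptly, on a 24-hour number, "in the event of any severe (Grade 3) local or systemic reactions". Grades are set by Tables 3 and 4. For swelling and redness, Grade 3 is 35 mm or more. For oral temperature it is 39.5°C / 103.1°F or more. None of these three carries a functional criterion.

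The participant's own instructions are in Appendix A. Under the heading on contacting the research team or doctor, severe (grade 3) symptoms are described as any that "prevents daily activity and/or requires medical care and/or missing work/school". The only fever action in Appendix A concerns a reading "at or above 100.0°F high, repeat approximately 20 minutes later to verify", with the highest value then recorded. It does not ask her to call.

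The protocol also provides safeguards:

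- In-person instruction at enrolment: "A study staff member will review each portion of the memory aid with the subject".
- Staff follow-up of web entries: "For severe symptoms in REDCap, study team will follow-up with the subject by phone".
- Scheduled contacts at Visits 2, 3, 5 and 6.
- Two lines in the Appendix A box inviting calls about anything that worries her.

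**The concern.** A woman can meet the protocol's definition of a severe reaction and still not meet the description she was given. Redness of 40 mm in someone who works as usual is the plain example: it is Grade 3 by Table 3, but outside the printed call rule unless she judges it to need care or is otherwise concerned.

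A prompt call lets staff arrange the unscheduled clinic visit for severe reactions. That visit includes vital signs, "direct measurement of the extent of local reactions, and photographs of local reactions", and notice to her provider. Measurement and photographs are most useful for reactions graded by size, and those are the local reactions the box leaves out. They also lose value with delay. Section 8.4.1 promises close follow-up for moderate to severe reactogenicity, and Section 5.4 designates no data safety monitoring board, so the participant's own report carries some weight here.

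The issue is timeliness of notification, not bias in the primary comparison.

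**Working it through.** The plan states no figure on this point to reproduce. The check is a comparison of texts, followed by visit-window arithmetic.

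**1. Items affected.** Table 3 lists 4 local items and Table 4 lists 11 systemic items: 4 + 11 = 15. Graded by measurement alone are swelling, redness and oral temperature, which is 3. For the other 15 − 3 = 12, the Appendix A wording agrees in substance with the tables.

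**2. Whether other participant material supplies the limits.**

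| Material | Temperature limit for calling | Size limit for calling |
|---|---|---|
| Appendix A, measurement instructions | None; repeat and record at 100.0°F | None |
| Appendix A, contact box | None | None |
| Appendices B, C, E (diaries) | None on the temperature row | None on the mm rows, which sit under a functional grade legend |
| Appendix D (simultaneous group, Visit 4) | None; the row reads "Post-Visit Day Date (dd/MM/yyyy) Oral Temperature °F" | Not applicable: no local rows, by design |
| Appendix F (phone script) | None; recorded readings are collected | None; non-zero entries are collected |

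The script's only severity question is functional: "Did any of your symptoms prevent you from doing your daily activities or going to work/school".

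**3. Possible delay for a paper-diary user who does not call.** From Section 5.1, Visit 2 falls on Days 3–5 and Visit 3 on Days 9–12. Delay = day of next contact − day of event.

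- Day 1 event: 3 − 1 = 2 to 5 − 1 = 4 days.
- Event just after a Day 3 call: 9 − 3 = 6 to 12 − 3 = 9 days.
- Event just after a Day 5 call: 9 − 5 = 4 to 12 − 5 = 7 days.
- Day 8 event: 9 − 8 = 1 to 12 − 8 = 4 days.

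In the sequential group, let Tdap be given on study Day T (22–29). Visit 5 is then at T+2 to T+4 and Visit 6 at T+8 to T+11. A vaccination-day event again waits 2–4 days. One just after the earliest Visit 5 call waits 8 − 2 = 6 to 11 − 2 = 9 days.

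**4. Scale.** The documents give no rate for Grade 3 swelling, redness or fever. Assuming, for scale only, that 1% to 10% of the 80 women have such an event: 80 × 0.01 = 0.8 and 80 × 0.10 = 8, or about 1 to 8 women. This is an upper frame, before removing REDCap users, women with a functional effect, and women who call out of concern.

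**5. Effect on the analysis.** Section 7.1.2 uses each woman's highest grade. Millimetres and °F are written down each evening, and Section 5.3 has solicited events classified by Tables 3 and 4, so the grade can be assigned from the recorded value whether or not she called.

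**The case against.** The strongest reply is that the instruction in Section 5.3 need not be delivered by the handout alone. Staff go through the memory aid with each woman, and use of the thermometer, ruler and diary is reviewed at Visit 1 and again at Visit 4, so the limits may be given verbally. The documents do not say whether they are. This leaves the practical consequence uncertain, but the printed rule still differs from the protocol's.

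Second, the box covers symptoms that require care, not only those for which care was sought, and it invites calls about any concern. Many women with 103.1°F would call on one ground or the other. That is fair, and it makes large but untroublesome local reactions the more realistic case. Even so, these routes depend on her judgement, whereas the protocol's trigger is the reading itself.

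Third, injection sites are scored against Tables 3 and 4 at least 20 minutes after vaccination (Section 5.2.3), and staff ask about symptoms as graded in those tables at Visits 2–3 and 5–6. The first check catches only immediate reactions. The second secures grading, but at the scheduled contact and no sooner.

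Fourth, Section 5.3 cites evidence that most reactions occur within 48 hours and that few start more than 3 days after vaccination. This point stands: the 6–9 and 4–7 day waits are uncommon worst cases, and the 2–4 day wait is the more typical one.

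**Conclusion.** The concern holds. For 3 of the 15 solicited items, the call rule handed to participants is narrower than the protocol's own definition of Grade 3, and nothing in Appendices A to F corrects it. This is a conflict between two stated rules, not a missing detail.

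The practical effect is small. It is confined to women, mainly on paper diaries, who reach a limit, carry on normally, see no need for care and are not concerned. For them staff may learn of the event days later, and the unscheduled visit may be late or missed. The number of such women cannot be estimated from the documents; the range of 1 to 8 rests on an assumed event rate and counts women before those exclusions. The conclusion also assumes that staff do not routinely state the limits aloud. Primary reactogenicity grading is largely unaffected. The change should be made because it concerns a safety instruction and costs little, but the trial's conclusions do not depend on it.

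**What to change.** Add two triggers to the Appendix A contact box: swelling or redness of 35 mm or more, and oral temperature of 103.1°F (39.5°C) or more. Print the temperature limit beside the temperature row in Appendices B to E, and the size limit beside the mm rows in Appendices B, C and E. In Appendix F, have the caller check each reported reading against the same limits.

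The cost is a revised handout, diary pages and phone script, with an IRB submission of those pages. No visits, data items or staff are added. The downside is a few more calls.
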